8.3.2 Safety

a) Anaphylaxis

The tracking label is shown in appendix 1. The data on the patient's tracking label must be transferred to the electronic case report form (eCRF) (see below) at the earliest opportunity, by research assistants in the emergency department, to mitigate against data loss.

8.4 Patients entered into pilot trial: In-hospital data collection

The following data are collected in-hospital.

8.4.1 Physiological parameters

The following measurements are collected on admission:

- a) Systolic, diastolic, and mean blood pressure
- b) Heart rate
- c) Shock index
- 8.4.2 Usability

The ease of sponge removal

- a) Unable to remove all sponges
- b) Reasonably easy to remove all sponges
- c) Sponges easily removed

The time required to remove the sponges

- a) 1 hour or longer
- b) Between 5 and 59 minutes
- c) Less than 5 minutes

The use of x-rays/image intensifiers to ensure complete removal of the sponges

- a) Imaging not used due to patient's clinical condition
- b) Imaging not used as not available
- c) Imaging deemed unnecessary
- d) Imaging used

Outcome of imaging:

- a) Additional sponges seen on imaging
- b) No additional sponges seen on imaging

Overall satisfaction with the device

- a) Dissatisfied
- b) Neither satisfied nor dissatisfied
- c) Satisfied

8.4.3 Blood tests

The following blood tests, which are all measured routinely as part of the clinical assessment of trauma patients, are collected, as soon as possible after admission:

- a) Blood lactate level (from arterial or venous blood gas measurement)
- b) Blood base deficit (from arterial or venous blood gas measurement)
- c) Hemoglobin/hematocrit, platelet count
- d) Prothrombin time (PT)/international normalized ratio (INR), activated partial thromboplastin time (APTT)/ratio
- e) Thromboelastograph (TEG) or thromboelastogram (ROTEM), if available

8.4.4 Survival

Time of death (if applicable)

8.4.5 Blood product/adjunct use

The amount of blood products used, over the first 24h since injury, are collected:

- a) Red cell concentrate (units)
- b) Plasma (units)
- c) Platelets (pools)
- d) Whole blood (units)
- e) Cryoprecipitate (units)

f) Tranexamic acid (grams)

8.4.6 Length of stay

- a) Intensive care (days)
- b) Hospital (days)

8.4.7 Safety

PhoXSTAT collects data on a number of prespecified safety events, over the first 7 days following injury, unless discharged earlier, including:

- a) Allergic reactions or anaphylaxis
- b) Wound infections (clinical diagnosis)
- c) Tissue damage thought to be related to the insertion of the device or deployment of the sponges (clinical diagnosis)
- d) Embolization of the sponges
- e) Inadvertent retention of sponges (beyond first operation)
- f) Non-therapeutic exploration

The above data are also to be entered into the eCRF as it becomes available.

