7.3 XSTAT safety (Objective 5)

Although XSTAT[®] is thought to be a low-risk device, we will nevertheless obtain formal data on its safety profile, which will include the following:

- a) Number of patients suffering allergic reactions or anaphylaxis
- b) Number of patients developing wound infections
- c) Number of patients developing tissue damage thought to be related to the insertion of the device or deployment of the sponges
- d) Number of patients suffering embolization of the sponges
- e) Number of patients who suffer inadvertent retention of sponges (beyond first operation)
- f) Number of patients in whom no vascular injury is identified

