8.5 Data collection schedule

The data collection schedule is summarized in table 1.

Table 1: Data collection									
Data	Pre- hospital	On admission	OR	6 hrs	24 hrs	7 days*	30 days*	Discharge	
Feasibility									
Lactate		~							
Blood pressure		~							
Heart rate		~							
Base deficit		~							
Hemoglobin		~							
Hematocrit		~							
Platelet count		~							
PT/INR		~							
APTT/ratio		~							
TEG / ROTEM		\checkmark							

Blood products					~			
Survival		~		~	~		~	~
Length of stay								~
Safety	~	~				~		
Usability	~		~					

*if still in hospital

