10.3 Safety

We will identify and report the individual and composite incidence of each of the a priori defined adverse events.

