13.2 Potential risks

The patients in the feasibility trial will be randomized to one of two treatment arms – XSTAT or standard care. Eligible patients for this trial will have been identified as having non-compressible (and therefore life-threatening) junctional injuries. As the randomization will take place at EMS unit level (rather than patient level), the risk of delaying treatment is negligible.

There is a possibility of some of the sponges, which form part of the device, being retained. This could occur because the sponges are not seen (at operation or on x-ray), or because they could not be located. Sponge retention could result in problems such as infection and pain.

There is also a theoretical possibility that the wound which the sponges are injected into is in continuity with the pleural or peritoneal cavities. This may result in the patient requiring an additional procedure or operation, to remove these sponges.

Lastly, it is possible that, despite the paramedics' best belief, the bleeding originated from tissue, rather than a vascular injury, and might have stopped, or did stop, without surgical exploration and repair. In this case, patients might require an operation which they might otherwise not have needed.

Overall, the risks of this study are deemed low.

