14.2 Reporting period

The reporting period includes any adverse events which occurred between randomization and discharge.

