14.3.2 Anticipated serious adverse events (SAE)/serious adverse device effects (SADE)

Anticipated adverse device effects include:

- a) XSTAT sponges left in situ after the index operation (either because they cannot be located, or because they were overlooked)
- b) XSTAT sponges which entered the peritoneal or pleural cavities
- c) XSTAT sponge embolization

Anticipated serious adverse events include:

- a) Need for surgical procedure to remove sponges, in the absence of a vascular injury requiring ligation or repair
- b) Death unrelated to XSTAT device
- c) Acute Kidney Injury
- d) Acute Lung Injury/Acute Respiratory Distress Syndrome
- e) Cardiac arrest
- f) Pulmonary embolus
- g) Extremity arterial thrombosis
- h) Multi-organ Failure
- i) Myocardial infarction
- j) Ventilator-Associated Pneumonia

Anticipated serious adverse events and adverse device effects will also be recorded using the "PHOXSTAT Adverse Event Recording Form". In addition, a "PHOXSTAT Serious Adverse Event/Serious Adverse Device Effect" form must be completed, and emailed to the PHOXSTAT Trial Office ([contact]) within 48 hours. All reports of anticipated SAE/SADE will be forwarded to the medical monitor.

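### Sections 8.4.7 and 14.2 set different safety windows, and section 10.3 does not say which one defines the Objective 5 incidence

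*Protocol*

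**What the plan says.** Objective 5 asks whether the device is associated with adverse effects. Protocol section 7.3 lists the outcomes for it, among them "Number of patients developing wound infections" and the number with sponges unintentionally retained past the first operation. It attaches no time window to any of them.

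Section 8.4.7 lists nearly the same events as prespecified safety events and collects them "over the first 7 days following injury, unless discharged earlier". In Table 1 (section 8.5) the Safety row has three marks, the last apparently in the 7-day column. That column carries the footnote "if still in hospital". The table layout is damaged in the copy reviewed, so the point rests on the text of 8.4.7.

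Section 14.2 sets another window: "The reporting period includes any adverse events which occurred between randomization and discharge". Section 14.3.2 names sponges remaining after the first operation as an anticipated adverse device effect.

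Section 10.3 promises the "individual and composite incidence of each of the a priori defined adverse events". It cites neither 8.4.7 nor section 14.

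**The concern.** The same patients can yield two different safety incidences, and the protocol does not say which one answers Objective 5. The phrase in 10.3 is closest to the prespecified list in 8.4.7, which carries the 7-day limit, but it speaks of adverse events, which is the term used in section 14. Either reading is open.

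The choice matters for events tied to material left in the wound. Section 13.2 warns: "Sponge retention could result in problems such as infection and pain". It also allows that a sponge may be seen neither at operation nor on x-ray, so some retention can come to light only afterwards. With at most 50 patients anticipated (section 9), one or two events more or less change the reported result. Section 3.3.1 gives the lack of safety data as a reason for the trial.

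**Working it through.** The protocol states no event rate, timing or power figure on this point, so there is no figure of its own to reproduce. The check compares the passages, and a labelled illustration follows.

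**Step 1. The rules side by side**

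| Section | Events | Window |
|---|---|---|
| 7.3 | Objective 5 list | none stated |
| 8.4.7 | prespecified safety events | 7 days from injury, or earlier discharge |
| Table 1 | Safety row | last mark apparently at 7 days, in-hospital only |
| 14.2 | any adverse event | randomization to discharge |
| 10.3 | events defined in advance | none stated |

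**Step 2. Four patients traced through the rules**

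| Wound infection or retained sponge first found | Counted under 8.4.7 | Recorded under 14.2 |
|---|---|---|
| Hospital day 5 | yes | yes |
| Hospital day 9 | no | yes |
| Day 6, at a return visit after discharge on day 3 | no | no |
| Day 20, at a return visit after discharge on day 12 | no | no |

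The second row is where the two rules disagree. The event has a place in the database: Form 12 in Appendix 2 takes a description, start date, relatedness and seriousness, has no day-7 limit, and allows events that are not on its code list. Section 14.3.1 requires non-serious events to be recorded as well. Only the tabulation is in doubt.

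The last two rows are lost under both rules. The mismatch does not cause that loss; it follows from ending collection at discharge.

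**Step 3. Illustration of what a short window does**

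Inputs: n = 25 XSTAT patients, half of the anticipated maximum of 50 (no allocation ratio is stated, so 1:1 is an assumption); true rate p, assumed 5% or 10%; share f of events falling inside the window, assumed 100% down to 25%.

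Chance of counting at least one event = 1 − (1 − p·f)^25.

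| p | f = 100% | f = 75% | f = 50% | f = 25% |
|---|---|---|---|---|
| 10% | 92.8% | 85.8% | 72.3% | 46.9% |
| 5% | 72.3% | 61.5% | 46.9% | 27.0% |

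For example, p = 10% and f = 50% gives 1 − 0.95^25 = 72.3%.

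If no event is counted in 25 patients, the one-sided 95% upper bound on the rate inside the window is 1 − 0.05^(1/25) = 11.3%. Divided by f, this corresponds to 15.1% overall if the window catches 75% of events (0.1129/0.75) and 22.6% if it catches half (0.1129/0.5).

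The documents supply neither p nor f. The table shows how the result would move, not how large the loss is.

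**The case against.** The strongest reply is that a list of events sought actively to day 7, alongside general reporting to discharge, is a workable design and not in itself a contradiction. An analysis plan that is not shown could name the window for 10.3. This stands in part: the in-hospital data exist, and a later document could choose. But 8.4.7 states a truncating rule for exactly the events that Objective 5 counts, and nothing in the protocol lifts it for the analysis.

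Three stronger readings are tempting and are not supported.

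- A reader might infer that the trial misses wound infections and retained sponges after day 7. It does not: while the patient is in hospital they are reportable under 14.2, and retained sponges are listed in 14.3.2.
- A reader might infer that the protocol itself treats these as late harms. It gives no timing. Its only retention figure, two of ten patients (section 5.2), came from the first x-rays after removal, which is early detection.
- A reader might infer a bias between the arms in favor of XSTAT, because controls could go home sooner without surgery. Section 7.2.2 does say the device commits the patient to exploration, but section 5.2 says that patients with these injuries typically undergo it anyway. If XSTAT patients did stay longer, they would be observed longer, which would tend to count against the device.

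It is also fair to say that this is a pilot without a primary outcome, and that in-hospital follow-up is a legitimate design choice.

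**Conclusion.** The point holds as an unresolved choice between two stated windows. If the 8.4.7 window feeds 10.3, in-hospital events after day 7 are recorded but left out of the prespecified incidence, which is then biased low. If the 14.2 window feeds it, that bias disappears. In both cases events first seen after discharge are not captured.

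The size is unknown, because the documents give neither the timing of events nor length of stay. A reader might be tempted to assume an infection risk and a late share and quote a shortfall. Any such figure would be unsourced, and one that treats everything after day 7 as lost would overstate it, since events between day 7 and discharge are recorded. The illustration above rests on assumed rates, assumed capture and 1:1 allocation.

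The conclusion does not depend on these harms being typically late, nor on any difference between the arms.

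**What to change.** In 8.4.7, Table 1 and 10.3, use one window for the prespecified safety events: randomization to discharge, as in 14.2. In Table 1 this needs only a Safety mark in the existing discharge column. Keep the day-7 count as a secondary display.

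Report length of observation by arm. A window that runs to discharge lets observation vary more with length of stay than a 7-day cap does, so this display and the day-7 count are needed beside it. The hospital days in section 8.4.6, and the arrival, discharge and death dates in Appendix 2, are already collected.

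State in 10.3 that events first seen after discharge are not captured.

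The cost is wording: 14.2 already requires the reports, so there is no extra data cost.

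Optionally, add events found in the participating centers' own records to day 30, where the IRB and the permission for continued participation (section 6.4.4) allow. The 30-day column in Table 1 does not provide this now, because it applies only to patients still in hospital. The cost is a chart review of at most 50 patients, and returns to other hospitals would still be missed.

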8.5 Data collection schedule

The data collection schedule is summarized in table 1.

Table 1: Data collection									
Data	Pre- hospital	On admission	OR	6 hrs	24 hrs	7 days*	30 days*	Discharge	
Feasibility									
Lactate		~							
Blood pressure		~							
Heart rate		~							
Base deficit		~							
Hemoglobin		~							
Hematocrit		~							
Platelet count		~							
PT/INR		~							
APTT/ratio		~							
TEG / ROTEM		\checkmark							

Blood products					~			
Survival		~		~	~		~	~
Length of stay								~
Safety	~	~				~		
Usability	~		~					

*if still in hospital

9. RECRUITMENT TARGETS

As PhoXSTAT is a feasibility trial, part of the rationale for which is to ascertain the number of eligible and recruitable subjects, there are no formal recruitment targets. An analysis of registry data from UAB suggests that there are around 10 patients per year who might benefit from XSTAT[®] application. On this basis, we anticipate enrolling a maximum of 50 patients, across the three PhoXSTAT sites, over two years.

10. STATISTICAL ANALYSIS

10.1 Feasibility

We will report the number of patients meeting the inclusion criteria, and the number of patients enrolled and randomized into the pilot trial.

10.2 Usability

This analysis will also be performed on intervention (XSTAT[®]) subjects only. We will report details for both categories.

10.3 Safety

We will identify and report the individual and composite incidence of each of the a priori defined adverse events.

10.4 Efficacy

We will compare the intervention (XSTAT[®]) and control groups, with regards to outcomes specified. As this is a pilot/feasibility study, no power or sample size calculation is required.

11. TRIAL MANAGEMENT

11.1 Trial office

The PhoXSTAT Trial Office is in the Center for Injury Science, University of Alabama at Birmingham, and provides support for the trial sites.

11.2 Project Management Group

The Program Manager takes responsibility for the day to day transaction of trial activities, such as site set-up and training, oversight of recruitment, etc. The PhoXSTAT Project Management Team meets at least weekly during the course of the trial to ensure smooth running and trouble-shooting.

11.3 Local organization in sites

Local PIs and research assistants are responsible for all aspects of local organization including identification of participants, data collection, and notification of any problems or unexpected developments for the duration of the trial. Specifically, participating sites will also be responsible for liaising with EMS agencies and providers, and for supplying and tracking trial intervention packs, including withdrawing packs which have expired.

Research assistants are responsible for ensuring that study data is collected and logged onto the remote web-based data capture system in a timely manner. The site agreement documents the full list of responsibilities for sites. Appropriate members of the local team must be fully conversant with the trial protocol and have Good Clinical Practice training. A delegation log is prepared for each site, detailing the responsibilities of each member of staff working on the study. This delegation log is kept at each site and at the Clinical Trial Center.

12. RESEARCH GOVERNANCE

12.1 Lead site

The Center for Injury Science at the University of Alabama at Birmingham is a Clinical Trial Center with expertise in running multicenter EFIC clinical trials in the prehospital and emergency department setting. The trial is run under the auspices of CIS aiding compliance with research governance and the principles of GCP and providing centralized trial administration.

12.2 Monitoring

The Principal Investigators ensure that adequate systems are in place for monitoring the quality of the trial and appropriate expedited and routine reports, to a level appropriate to the risk assessment of the trial. CIS's Standard Operating Procedures will be followed.

12.3 Relationship with the manufacturer of the XSTAT[®] device

The manufacturers of the XSTAT[®] device (RevMedx[™]) have no role in the design, conduct, analysis, or reporting of the trial. The relationship between XSTAT[®] and the trial staff is governed by a Clinical Supply Agreement. We have developed a close working relationship with RevMedx[™] and will liaise with the company regarding any safety issues.

12.4 Data protection

Data collected during the course of the research will be kept strictly confidential and accessed only by members of the trial team. Participant's details are stored on a secure database and regular checks and monitoring are in place to ensure compliance. The data manager (in collaboration with the Principal Investigators) manages access rights to the data set. Participants are allocated an individual specific trial number and their details are anonymized on the secure database.

13. HUMAN SUBJECTS RESEARCH

13.1 FDA Requirements

This study will enroll approximately 50 patients with Penetrating junctional injuries. The study intervention (XSTAT[®] 12) is approved by the Food and Drug Administration (FDA) as a Class II nonsignificant risk medical device under 21 CFR 878.4452 "Non-absorbable expandable hemostatic sponge for temporary internal use." Although it is a nonsignificant risk device being used in accordance with its defined indications, we are required to seek an FDA Investigational Device Exemption (IDE) because it is used in this setting in accordance with the regulations for exception from informed consent.

13.2 Potential risks

The patients in the feasibility trial will be randomized to one of two treatment arms – XSTAT or standard care. Eligible patients for this trial will have been identified as having non-compressible (and therefore life-threatening) junctional injuries. As the randomization will take place at EMS unit level (rather than patient level), the risk of delaying treatment is negligible.

There is a possibility of some of the sponges, which form part of the device, being retained. This could occur because the sponges are not seen (at operation or on x-ray), or because they could not be located. Sponge retention could result in problems such as infection and pain.

There is also a theoretical possibility that the wound which the sponges are injected into is in continuity with the pleural or peritoneal cavities. This may result in the patient requiring an additional procedure or operation, to remove these sponges.

Lastly, it is possible that, despite the paramedics' best belief, the bleeding originated from tissue, rather than a vascular injury, and might have stopped, or did stop, without surgical exploration and repair. In this case, patients might require an operation which they might otherwise not have needed.

Overall, the risks of this study are deemed low.

13.3 Protection of human subjects

The reasons for conducting an EFIC trial are outlined in section 6.4. A detailed explanation of each criterion stipulated in the regulations for this exception and how our trial design applies to these criteria is outlined in Appendix 3.

14. ADVERSE EVENT/EFFECT REPORTING

The XSTAT device is FDA approved, has been in use for some time, and its safety profile is well established.(7) Nevertheless, it is possible that adverse events may occur, and the trial will collect data on adverse events that may be associated with the use of XSTAT. Adverse events will be reviewed by the sponsor, which is the Department of Defense.

14.1 Definitions and classification

All untoward medical occurrences will be classified by:

- a) Whether they involved a trial participant
- b) Were related to the use of the device
- c) Seriousness
- d) Whether anticipated/unanticipated.

Note that adverse *events* are non-device-related medical occurrences, whereas adverse *effects* are caused by the investigational device or procedure.

14.1.1 Untoward medical occurrence

An untoward medical occurrence is an unintended disease or injury or untoward clinical sign in a trial participant caused by or related to the investigational device, device-related procedure, or comparator. Not all complaints about investigational devices have to do with untoward medical occurrences. If a complaint does not involve a trial participant or other person, it is not medical and is called a "non-medical complaint." Non-medical complaints do not need to be logged.

14.1.2 Adverse events

If the untoward medical occurrence did involve a trial participant, but was not related to the device, it is an adverse event. These events are further classified as serious adverse events (SAE) or non-serious adverse events (AE).

14.1.3 Serious adverse events

Serious adverse events are untoward medical occurrences in a subject that are not related to the investigational device, comparator, or trial procedures, but that meet the criteria of "serious." A serious adverse event is one that:

- a) Led to a death
- b) Led to a serious deterioration in the health of the subject that:
 - i. Resulted in a life-threatening illness or injury, or
 - ii. Resulted in a permanent impairment of a body structure or a body function, or
 - Required in-patient hospitalization or prolongation of existing hospitalization, or
 - Resulted in medical or surgical intervention to prevent life threatening illness or injury or permanent impairment to a body structure or a body function
 - v. Led to fetal distress, fetal death, or a congenital abnormality or birth defect.

A planned hospitalization for a pre-existing condition or a condition required by the protocol, without serious deterioration in health, is not considered serious.

